4.3. Secondary Endpoints

Comparison of the detection of each type of arrhythmia between the two devices

- Comparison of the duration of the examination between the two devices;
- Comparison of mean, minimum, and maximum heart rate captured between the two devices;
- Comparison of the total atrial ectopic heart beats captured between the two devices;
- Comparison of total ventricular ectopic heart beats captured between the two devices;
- Comparison of total episodes of supraventricular tachycardia, ventricular tachycardia, and pauses between the two devices;
- Evaluate the convenience of using the two registration systems.

The individual categorical secondary endpoints (detection of each type of arrhythmia) will also be evaluated by diagnostic statistics (accuracy, sensitivity, specificity, positive and negative predictive values) with respective 95% confidence intervals.

The continuous secondary endpoints (mean, minimum and maximum heart rate, total atrial and ventricular ectopic heart beats, total episodes of supraventricular tachycardia, ventricular tachycardia and pauses) will be described by Bland-Altman plots accompanied by Lin and Pearson correlation coefficients.

Lists with the patient's reports will be made to evaluate the convenience of the systems. The Chi-square test or Fisher's exact test will be used to evaluate the

proportion of patients who report greater comfort (comfort of the device) with *Quoreone* versus *Cardiolight*.

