## 2.3. Sample Size

The sample size calculation of the study was established assuming the hypothesis of comparability of the *QuoreOne* device in relation to the conventional device. According to data from a previous study, we have:

		Holter Any 6 (24 h)		Total
		No	At least 1	
Patch any 6 (24 h)	No	83	11	94
	Yes	2	50	52
Total		85	61	146

Any arrhythmias (of the 6 types atrioventricular block, pause, polymorphic ventricular tachycardia, supraventricular tachycardia, ventricular tachycardia, or atrial fibrillation)

From the data in the table above, we obtain the following proportions:

		Holter Any 6 (24 h)		Total
		No	At least 1	
Patch any 6 (24 h)	No	0.5685	0.0753	0.6438
	Yes	0.0137	0.3425	0.3562
Total		0,5822	0.4178	1.0000

Assuming that *QuoreOne* and Holter will agree to detect at least one arrhythmia event similar to that found between Patch and Holter in the reference study, a sample of 182 patients will have 80% power to show that the overall accuracy is greater than 85%, at a one-tailed significance level of 2.5%. (i.e., the lower limit of the 95% confidence interval (CI) should be above 85%). Therefore, this premise considers Holter as the "gold standard" test, and the accuracy of the *Quoreone* is evaluated in the detection of global arrhythmias (primary endpoint) and specific categories (secondary endpoints).

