#### 3.3. Analysis Populations

All individuals of both sexes, aged 18 years or older who use both systems simultaneously for 24 hours, present complete data in both examinations and have signed the consent form will be part of the Full Analysis Set (FAS).

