### Secondary Outcomes

The individual categorical secondary endpoints (detection of each type of arrhythmia) will also be evaluated by diagnostic statistics (accuracy, sensitivity, specificity, positive and negative predictive values) with respective 95% confidence intervals.

The continuous secondary endpoints (mean, minimum and maximum heart rate, total atrial and ventricular ectopic heart beats, total episodes of supraventricular tachycardia, ventricular tachycardia and pauses) will be described by Bland-Altman plots accompanied by Lin and Pearson correlation coefficients.

Lists with the patients' reports will be made to evaluate the convenience of the systems. The Chi-square test or Fisher's exact test will be used to evaluate the proportion of patients who report greater comfort (comfort of the device) with *Quoreone* versus *Cardiolight*.

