### 5.3. Missing Data

No imputation will be performed and only analysis of complete data will be performed.

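### Agreement statistics for SVT, VT and pause counts are taken over all patients, so pairs with zero episodes on both devices dilute them and they do not describe patients who have episodes

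*SAP*

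**What the plan says.** Protocol 4.3 lists among the secondary endpoints the "Comparison of total episodes of supraventricular tachycardia, ventricular tachycardia, and pauses between the two devices". Protocol 4.3 and SAP 5.2 put these counts in one list with heart rates and ectopic-beat totals and give them all the same treatment: "total episodes of supraventricular tachycardia, ventricular tachycardia and pauses) will be described by Bland-Altman plots accompanied by Lin and Pearson correlation coefficients".

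The SAP defines one population. Under SAP 3.3, patients who use both systems for 24 hours, "present complete data in both examinations and have signed the consent form will be part of the Full Analysis Set (FAS"). SAP 5.3 adds: "No imputation will be performed and only analysis of complete data will be performed". A count of zero is a complete value, so it stays in. Neither document mentions a subset of patients with episodes, a transformation, or a method for counts with many zeros.

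Detection of each arrhythmia type is assessed separately, by diagnostic statistics (SAP 5.2) and Cohen's kappa (SAP 5.4). SAP 5.2 also has every measure summarised for each device with the descriptive statistics of SAP 4.5.

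**The concern.** Every patient has a heart rate, but many have no VT run or pause in 24 hours. A patient with no episodes on either device contributes a difference of exactly zero and tells us nothing about how well episodes are counted when they occur. With many such patients, the mean difference and limits of agreement describe a mixture: they are too wide for patients without the arrhythmia and usually too narrow for those with it. Lin's and Pearson's coefficients gain from the contrast between the zero and non-zero groups, even if the counts within the non-zero group agree poorly.

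At stake is what the report can say about episode counts. This is the only planned paired analysis of them, because sensitivity and kappa use yes/no detection. A device that found 3 of 10 VT runs in every affected patient would have full sensitivity for VT.

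**Working it through.** **The plan's own figures.** The documents give no figure for the agreement analyses. The planning table in SAP 2.3, labelled "Any arrhythmias (of the 6 types atrioventricular block, pause" and so on through the six types, has 83 of 146 patients negative on both devices: 83/146 = 0.5685, as printed. Planned accuracy is (83 + 50)/146 = 0.9110. With that value, 182 patients and a Wald 95% lower limit above 85% (at least 163/182 correct), exact power is 80.7%, in line with the stated 80%. A Wilson or Clopper-Pearson limit would give 64.4%, which is a separate matter. So this table is the one the sample size rests on.

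**Share of double zeros.** The six types include SVT, VT and pauses. A patient negative for all six on both devices is a 0-0 pair for each of them, so each type has at least 56.8% double zeros. The share q with an episode on either device is at most 63/146 = 0.432.

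**Effect on bias and limits.** Let the paired differences among affected patients have mean b and SD s. Over all patients:

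- mean difference = q·b
- variance = q·s² + q(1 − q)·b²

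At q = 0.432 the mean difference falls by at least 57%. The SD relative to s is:

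| q | b = 0 (ratio √q) | b = −3, s = 3 |
|---|---|---|
| 0.432 | 0.66 | 0.82 |
| 0.20 | 0.45 | 0.60 |
| 0.10 | 0.32 | 0.44 |

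For b = −3, s = 3 and q = 0.432: variance = 0.432·9 + 0.432·0.568·9 ≈ 6.09, SD 2.47, limits −1.29 ± 4.84 = (−6.1, 3.5). In affected patients alone they are −3 ± 5.88 = (−8.9, 2.9).

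The limits widen instead when q·s² + q(1 − q)·b² > s², that is, when |b|/s > 1/√q. At q = 0.432 this is 1.52, so it needs a miscount that is nearly constant across affected patients.

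**Effect on Lin.** Suppose the two devices' counts are unrelated within affected patients, each geometric with mean 6 and variance 30 (assumed). The true coefficient among them is 0. Over all patients the covariance is q(1 − q)·36 and each variance is 30q + q(1 − q)·36. At q = 0.432 this gives 8.83/21.78 = 0.41; at q = 0.10, 3.24/6.24 = 0.52.

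**Illustration.** Assumptions: affected patients have 1 plus a Poisson-gamma count (mean 9, shape 0.7), and QuoreOne finds each episode with probability 0.7.

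| q | Bias, all | Width of limits, all | Lin, all | Affected patients inside the all-patient limits |
|---|---|---|---|---|
| 0.432 | −1.3 | 11.0 | 0.92 | 87% |
| 0.10 | −0.30 | 5.7 | 0.93 | 70% |
| 0.05 | −0.15 | 4.1 | 0.93 | 60% |

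In affected patients alone, bias is −3.0, width about 14.3 and Lin 0.89.

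**Do the all-patient statistics still respond to poor counting?** They do. In the same model at q = 0.10, the width is 5.7, 9.3, 12.8 and 14.6 and Lin is 0.93, 0.79, 0.53 and 0.37 when 70%, 50%, 30% and 20% of episodes are found.

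**The case against.** A reader might infer that the planned statistics would look good however badly episodes are counted, or that a device losing a large share of them would still show Lin above 0.9. Neither holds. Bias, limits and Lin all worsen with the miscount. In the example Lin exceeds 0.9 at 30% loss, but at 50% loss it is 0.76 to 0.79. Nor do the limits always shrink.

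Other points on the plan's side:

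- The zero share comes from another study. It is least certain for SVT, which here means runs of three or more beats in an arrhythmia clinic; the SAP does not give the reference study's definition. However, the sample size assumes that QuoreOne and Holter "will agree to detect at least one arrhythmia event similar to that found between Patch and Holter in the reference study", so the table is a fair planning basis.
- A Bland-Altman plot shows individual pairs, and 0-0 pairs collapse at the origin. The device means expose relative loss, since zeros dilute both equally: 1.0 against 0.7 in the 10% example. Both help, but the means do not show agreement within patients, and the limits and coefficients remain diluted.
- No acceptance limit is set for these statistics. A false verdict of comparability is therefore possible but not built into the plan.
- All-patient limits answer a legitimate question about a consecutive referred patient. Restricting to patients positive on either device selects on the outcome and is less precise: at 10% affected, only about 18 of 182 remain. This stands, and is a reason to add the restricted analysis, not to replace the planned one.

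**Conclusion.** The concern holds in a limited form. As written, the agreement statistics for SVT, VT and pause counts do not describe count agreement in patients who have episodes. On the planning data the mean difference is reported at no more than 0.43 of its value in those patients. The limits are usually narrower than theirs: 66% of the width or less with no mean bias, and 82% at q = 0.432 with b = −3 and s = 3. Lin is pushed upward.

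Only q ≤ 0.432 comes from the documents, and it assumes that this trial resembles the reference study. Smaller shares and all count distributions are assumptions. At the documented share the distortion is moderate (87% of affected patients inside the nominal 95% limits in the example); it becomes large only for rarer types.

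Severity is minor. The endpoint is secondary and descriptive, and the primary criterion, accuracy above 85%, is not touched.

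**What to change.** In SAP 5.2, for episodes of SVT, VT and pauses:

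- keep the planned all-patient statistics and report beside them the Bland-Altman, Lin and Pearson statistics in patients with at least one such episode on either device;
- state the number of those patients and the number of 0-0 pairs for each type;
- base any statement on count agreement on the restricted version;
- where too few patients are affected for meaningful limits, list the paired counts instead.

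A log or ratio scale alone would not cure this, because the 0-0 patients would still enter.

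The change needs SAP wording only and uses the same data. The cost is smaller denominators and wider, less precise limits, with a listing in place of limits for rare types.

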1.4.2 Secondary Objective

Compare the 24-hour electrocardiographic recordings detected by both systems. The following will be included in the analysis: a) maximum, minimum and mean heart rates; b) total atrial and ventricular ectopic heart beats; c) episodes of supraventricular tachycardia, ventricular tachycardia, and pauses. In addition to these variables, the duration of the examination and the convenience of using both systems should also be compared.

2. Materials and methods

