## 2. STUDY METHODS

### 2.1. Study Design

This is a comparative, single-center study with consecutive inclusion of patients. Research participants will be included prospectively.

All exams will be performed at IDPC, the exams performed with the *Cardiolight* equipment will be stored both in the original file (.xcm) and in the final version of the report (.pdf). The exams performed with the *QuoreOne* equipment will be saved directly on the online report platform and in the final version of the report (.pdf). These files will be exported to an external hard drive and sent for tabbing. The parameters will be analyzed with anonymized data from the participants.

After the Holter devices are removed, the participant will be asked to answer a questionnaire about the convenience of use and functions of the *QuoreOne* device.

The Holter-type cardiac monitor is a portable ambulatory electrocardiography device. It aims to monitor the electrical activity of the heart over a prolonged period, usually twenty-four hours.

For this study, the *Cardiolight* recorder from the company Cardios, the predominant equipment in the medical practice of the IDPC, and the *QuoreOne* recorder, from Quoretech, will be used, which will be submitted to comparison.

The exams performed by the conventional system (*Cardiolight*, Cardios) will be analyzed and the reports released by physicians from the Electrophysiology Section of the IDPC. These tests will be implemented at the same time in the same patient and for the same duration. The physicians evaluating the results of one method will be the same as the physicians evaluating the results obtained by the other method, but these will be blinded to the patients' data, making it impossible to identify that the tests being evaluated are from the same patient.

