## 2.2. Randomization

This is a comparative, single-center study, where all patients included consecutively and prospectively, will use both systems simultaneously, Quoretech's *QuoreOne* and Cardios' *Cardiolight*. In this way, it will not be necessary to use any randomization technique.

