#### 2.6. Moments of Evaluation of Results

The exams performed by the conventional system (*Cardiolight*, *Cardios*) and the *QuoreOne* system will be implemented at the same time in the same patient and for the same duration. The monitoring of the electrical activity of the heart during a period of approximately 24 hours will be done by the systems, which will record the records at times according to the custom of medical practice.

The parameters will be analyzed with anonymized data from the participants.

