### 3. STATISTICAL PRINCIPLES

#### 3.1. Confidence Intervals and p-Values

Two-tailed hypothesis tests with a significance level of 5% and confidence intervals of 95% will be used.

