### 5.4. Additional Analytics

The evaluation of agreement between the devices will also be performed from the Cohen Kappa statistic for the primary endpoint, and each of the secondary endpoints (arrhythmias criteria one by one).

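### Device comfort is rated by patients who all wear both recorders, yet the named tests, Chi-square or Fisher's exact, are for independent groups

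*SAP*

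**What the plan says.** SAP 5.2 (Secondary Outcomes) states, for QuoreOne versus Cardiolight: "The Chi-square test or Fisher's exact test will be used to evaluate the proportion of patients who report greater comfort". Protocol 4.3 carries the same sentence. Both also promise lists of patients' reports.

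The design has one group. SAP 2.2 says that all patients "will use both systems simultaneously", and SAP 2.6 says that the two exams are "implemented at the same time in the same patient and for the same duration".

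SAP 3.1 sets the error rate: "Two-tailed hypothesis tests with a significance level of 5% and confidence intervals of 95% will be used". SAP 5.4 adds Cohen's kappa, but only for the primary endpoint and "each of the secondary endpoints (arrhythmias criteria one by one"), so it does not reach comfort.

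On the source of the data, SAP 2.1 and Protocol 2.5 say that after removal of the devices "the participant will be asked to answer a questionnaire about the convenience of use and functions of the" QuoreOne device. Protocol 1.4.2 says that "the convenience of using both systems should also be compared". Neither document gives the wording of the comfort item or its answer options.

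**The concern.** A two-way Chi-square or Fisher's exact test assumes that its rows are separate sets of people. Here the two rows would be the two devices, worn by the same patients. The answers are then either one preference per patient or a pair of ratings per patient, and both need a different test.

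A one-sample Chi-square against 50% would be valid for a preference item. The plan states no 50% reference, however, and it offers Fisher's test as the alternative. Fisher's test needs a two-way table, so a device-by-answer table is the natural reading, though not the only one.

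The stake is one tested secondary endpoint in a study funded by the maker of QuoreOne. A comfort advantage for either device could be declared at the 5% level from a split that a valid test would not call significant.

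**Working it through.** **The plan's own figure.** The documents give no power or sample size for comfort. The 182 in SAP 2.3 is for overall accuracy. With an assumed accuracy of (83 + 50)/146 = 91.1% and a lower Wald 95% limit above 85% as the success rule, at least 163 agreements of 182 are needed, and exact power is 80.7%, close to the stated 80%. Comfort does not enter that calculation. Below, 182 serves only as the number of patients answering, tested two-sided at 5% (SAP 3.1).

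**Case 1: one preference per patient, forced choice.** Let x of n = 182 prefer QuoreOne.

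- One-sample Chi-square: (2x − n)²/n.
- Two-device table, rows (x, n − x) and (n − x, x): 2(2x − n)²/n, exactly twice as large because each patient is counted twice.

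At x = 101, 2x − n = 20. The one-sample statistic is 400/182 = 2.198 (p=0.138), and the two-way statistic is 4.396 (p=0.036).

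| Split | Two-way Chi-square p | Fisher p | Exact binomial p |
|---|---|---|---|
| 100 v 82 | 0.059 | 0.075 | 0.208 |
| 101 v 81 | 0.036 | 0.046 | 0.159 |
| 104 v 78 | 0.0064 | 0.0087 | 0.064 |
| 105 v 77 | 0.0033 | 0.0046 | 0.045 |

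The two-way tests first reject at 101 and the exact binomial at 105, so conclusions differ at 101 to 104 and at the mirror splits. At 101/182 = 55.5% the exact 95% CI is 48.0% to 62.8%.

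Summing the Binomial(182, 0.5) probabilities over each rejection region gives the true type I error: **15.9% for two-way Chi-square and for Fisher; 4.5% for the exact binomial and for the one-sample Chi-square**. The large-sample value for the two-way test is 2[1 − Φ(1.96/√2)] = 16.6%.

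**Case 2: some patients state no preference and stay in the denominator.** If q is the share preferring each device under no difference, the difference of the two shares has variance 2q/n. The two-group test assumes 2q(1 − q)/n, which is too small by the factor 1 − q. The excess therefore fades as q falls. By exact enumeration over an assumed range:

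| No preference | Chi-square | Fisher | Exact binomial |
|---|---|---|---|
| 20% | 12.5% | 10.6% | 4.1% |
| 40% | 10.0% | 8.3% | 4.0% |
| 60% | 8.0% | 6.1% | 3.8% |
| 70% | 7.2% | 5.2% | 3.7% |
| 80% | 6.2% | 4.2% | 3.3% |
| 90% | 5.4% | 3.2% | 2.9% |

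Example with 36 no-preference answers (182 − 36 = 146): 83 v 63 gives Chi-square p=0.032, Fisher p=0.042, exact binomial p=0.12.

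**Case 3: each device rated separately, comfortable yes or no.** With within-patient correlation ρ, the large-sample error of the two-group Chi-square is 2[1 − Φ(1.96/√(1 − ρ))]. Simulation (200,000 runs each, assumed 70% comfortable on each device):

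| ρ (assumed) | Chi-square | Fisher | Exact McNemar |
|---|---|---|---|
| −0.2 | 7.2% | 5.8% | 3.9% |
| 0 | 5.0% | 3.8% | 3.8% |
| 0.3 | 1.9% | 1.4% | 3.7% |
| 0.5 | 0.55% | 0.32% | 3.4% |

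The assumed rate matters little: at ρ = 0, 0.3 and 0.5, Chi-square gives 5.1%, 2.0% and 0.6% for a 50% rate, and 5.0%, 1.9% and 0.6% for a 90% rate.

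**The case against.** The best defence is that the sentence speaks of a single proportion, those who find one device more comfortable than the other, and that Chi-square can mean a one-sample test against 50%, which holds its level at 4.5%. On that reading the test is under-specified rather than wrong. This stands as a possible reading of the Chi-square half of the sentence. It cannot cover Fisher's test, and the text would need correcting even so.

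Second, 15.9% needs a preference item, no neutral option, and an analyst who enters each patient under both devices. The documents state none of these. This is right: 15.9% is an upper case, and for separate ratings with positive correlation the error runs the other way, so the loss there is power rather than false positives.

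Third, the choice of test rarely matters when the preference is strong. Under forced choice the chance of landing in the disputed 101 to 104 range is 22% for a true preference of 55%, 14% for 60%, 1.4% for 65% and about 0.015% for 70% (assumed values). This also stands. The harm is concentrated where preference is weak or absent, which is where a 5% error rate is meant to protect.

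Fourth, the questionnaire form is not among the documents, so a description centred on QuoreOne does not show that no comparative item was asked. Agreed; that part is a request for clarification.

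**Conclusion.** The concern holds. For data that are one-sample or paired by design, the plan names tests for independent groups, and nothing elsewhere in either document repairs this. The mismatch is certain, but its size and direction depend on the unstated answer format:

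- With a preference item in a two-device table, Chi-square exceeds 5% throughout the range examined, from 15.9% under forced choice to 5.4% at 90% no preference. Fisher falls below 5% from about 80%.
- With separate ratings, Chi-square is correct at zero correlation, liberal below it and conservative above it.

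These figures assume 182 respondents and no true difference. The no-preference shares, the correlations and the comfort rates are assumptions. The matter should be fixed, but it reaches only the comfort endpoint; the primary accuracy analysis and the sample size do not depend on it.

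**What to change.** In SAP 5.2 and Protocol 4.3:

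1. State the comfort item and its answer options.
2. For a preference item, replace Chi-square/Fisher with an exact binomial (sign) test against 50% among patients who state a preference. Report the proportion with its 95% CI and the number with no preference.
3. If the devices were rated separately as yes/no, use exact McNemar with the paired difference and its 95% CI.
4. If a one-sample Chi-square against 50% was meant, say so and delete Fisher's test.

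In SAP 2.1 and Protocol 2.5, reconcile the questionnaire described as being about QuoreOne with an endpoint that compares two systems. If no comparative or Cardiolight item was collected, report QuoreOne comfort descriptively, without a test.

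The cost is a few sentences, with no new patients and no change to the 182. The comfort p-value may become less favourable (0.036 becomes 0.16 at 101 v 81). The schedule in Protocol 7 shows data collection ending in November 2021, before protocol version 4.0 of 25 February 2022, so an item that was not asked could probably not be added now. The test should be settled from the questionnaire form, not from the answers.
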